
1. Primary outcome measure: a.VAS pain intensity differences from baseline among the groups at each time point and maximum pain relief.
 
b.Bite Force measurement using the Bite Fork at baseline, 1.5 h, 3h and 7d.
 
2. Secondary outcome measure: Measure psychoactive effects, mood changes at 0, 1.5h and 3h points, and somnolence at 3h and 1- week time point.
	
1. Patients will report their pain level using a 100mm Visual Analogue Scale (VAS) at 0, 15min, 30min, 45min, 1h, 1.5h, 2 and 3 hour and 1week post-administration visit time of study drug Epidiolex or Placebo.
 
2. Patients will report their pain level that is elicited by biting down on the Bite Fork at 0, 1.5h, 3h and 1week post-administration visit time of study drug Epidiolex or Placebo.
 
2. Patients will report feelings of drug high, alterations in internal perception and alterations in external perception, along with alertness, contentment and calmness by completing the following questionnaires:
 
a. Bowdle questionnaire b. Bond & Lader Mood Scale c. Epworth Sleepiness Scale
	
1. The VAS has been shown to be sensitive to changes in a patient's pain experience, is easily understood and easy to use. It has been successfully used in various health fields in children and adults.
 
2. The bite force measurement provided additional pain information being able to isolate one particular tooth (the problem tooth) being studies.
 
2. The three listed questionnaires are commonly used for psychedelic assessment and safety assessment of cannabinoids use, with a longstanding administration in previous published studies in medical journals such as "Pain", "CNS Drugs", and "Journal of Psychopharmacology". Such effects are not commonly associated with CBD use because of the inherent nature of the absence of THC based on current literature. Nevertheless, patients that report such adverse events at the end of the observation period will be asked to have a family member to accompany them home.

4. Rationale Briefly state the reason for conducting the clinical trial.			

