Adults 18-75 years old with moderate-severe odontogenic pain	
 -Healthy adults 18-75 years old, ASA I or II. -Permanent tooth with moderate to severe odontogenic pain, i.e. ≥30 on a 100mm VAS, as reported verbally by the patient. -Clinical pulpal diagnosis of irreversible pulpitis or pulpal necrosis, and periapical diagnosis of symptomatic apical periodontitis. -Test negative for recent cannabis use and/or other drugs of abuse including alcohol (urine tests collected at screening visit. Results will be available on site within 3-5 minutes). -Participant able to understand the forms (English or Spanish) and provide informed written consent 	
 -ASA Class III or IV, patients with hepatic impairment, pregnant or lactating women (pregnancy test is performed at the screening visit). -Patients on drugs metabolized by enzymes that also metabolize CBD (e.g. clobazam, diazepam, topiramate, warfarin), or other drugs known to interact with Epidiolex (as assessed by PI at time of screening). -Self-reported prior experience inhaling cannabis (either via smoking or vaporization). -Use of opioids in the month prior to screening/treatment visit, and/or NSAIDS or acetaminophen 6 hours prior to treatment. -Unwilling to participate
6.4. Will screen failures be allowed to re-screen at a later date?	 No  Yes If yes, describe criteria below ↓	Since the patients present with emergency pain and their pain will need to be addressed in a timely manner with appropriate treatment, there won't be any re-screening.

7. Study Intervention(s) being tested or evaluated

This can include prevention, diagnostic or therapeutic interventions (e.g., drug or device) or educational, health services or basic science interventions (e.g., educational program, health care delivery model, or examining basic physiology)

This is a therapeutic intervention study where the FDA approved study drug used off-label in two different doses according to randomization will be assessed against a Placebo of similar taste and appearance.

Group 1: CBD 10mg/kg single dose (given one time only) Epidiolex 100mg/ml oral solution

Group 2: CBD 20mg/kg single dose (given one time only) Epidiolex 100mg/ml oral solution

Group 3: Placebo oral solution single dose (given one time only)

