The objective here is to test Epidiolex off-label for the treatment of emergency tooth pain in a human clinical trial. We hypothesize that Epidiolex will provide substantial pain relief for the patients presenting with emergency odontalgia in our clinical research facility.

Patients who present to the UT dental clinics will be provided a standard of care dental exam assessing the oral problem that brought them to the clinic. A non-research, routine oral exam will be provided. If the patient has expressed pain as part of their dental problem, they will be approached by study staff to explain the study and inquire if the patient would be interested in entering the study. If interested, informed consent will be obtained and documented. Medical history, demographics, vitals, pain questionnaire, Bite Force measurement, and study oral exam will be completed. Height & weight of the patient will be obtained for calculation of study medication to be given. Screening labs (urine pregnancy test for women of child-bearing age and urine toxicology) will be completed for research purposes to confirm inclusion/exclusion criteria. Subjects who meet all eligibility criteria will proceed to randomization. Eligible subjects will be randomized in a 1:1 ratio to one of the three study intervention arms: Epidiolex 10mg/kg, Epidiolex 20mg/kg or Placebo. Rescue pain medication of Ibuprofen 600mg or Acetaminophen 500mg will be administered if needed. Pain, Psychoactive and sleep questionnaires will be completed following study intervention administration at the timepoints outlined in the schedule of events. A follow-up research visit will occur one-week post-drug administration where a research sleep questionnaire will be completed and oral exam data collected (pain assessment, reported issues post-treatment, any rescue medication used).

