2. Self-reported prior experience inhaling cannabis (either via smoking or vaporization). Cannabis trials often present with high placebo effect. Cannabis naïve subjects are thus proposed to minimize this effect as well the possibility of tachyphylaxis.

3. Use of opioids in the month prior to screening/treatment visit, and/or NSAIDS or acetaminophen 6 hours prior to treatment. Any analgesic can potentially mask the effects of the study drug and increase placebo effect.

Continued Study Monitoring and Halting Rules:

Study drug is administered one time only at study hour zero with monitoring for the next three hours. Once the assigned study drug is given, the subject will continue in the 3-hour study observation period, even if they request the rescue medication. Only if they specifically request to formally withdraw from the study will they proceed to the dental treatment early, however subjects will be asked to complete the 3rd hour pain and Psychoactive Assessment Questionnaires at the time of consuming the rescue medication. Each patient is different in regards to their pain endurance level, so subjects will be instructed to request rescue medication when their pain becomes uncomfortable. Subjects will be encouraged to wait at least 60 minutes after the one time administration of the study drug before consuming any rescue medication. Subjects will additionally be asked to attend the one-week follow-up visit and complete the VAS and Sleepiness Scale Assessment.

In the case that a serious event appears within the same arm more than three times, we will discontinue the arm of the study. The PI will unblind the cases for close monitoring of the adverse event.

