12.2. Sample Size Determination

Include number of participants to recruit, screen, and enroll to have adequate power to test the key hypotheses for the study. Provide all information needed to validate your calculations and judge the feasibility of enrolling and following the necessary number of participants.

This is a pilot clinical trial to determine the necessary effect size for an appropriately powered definitive clinical trial that will be pursued in a subsequent R01 (or UG3/UH3) application submitted to the NIH. We plan to enroll a convenience sample of N=22/group. We note that prior definitive studies in this pain model have detected NSAIDs such as ibuprofen with a similar sample size (17, 18).

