12.3. Populations for Analyses

Clearly identify and describe the analysis datasets (e.g., which participants will be included in each).

All participants in all three groups will be included in the analyses. The 3 groups will be compared to each other. While we expect that randomization will lead to balanced groups, we will specifically assess for age and sex balance and perform sensitivity analyses, if indicated. Further, we will employ generalized estimating equation models accounting for correlation between pain measures at various timepoints to assess the timepoint when maximum analgesia is observed.

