12.4. Statistical Analyses

Include analysis of primary efficacy endpoints, secondary endpoints, safety analyses, and any planned interim analyses

This analysis will provide critical information for subsequent sample size calculations and endpoint determination in the subsequent main study. Mixed model analyses will be used for both primary and secondary outcomes. AEs among the groups will be analyzed with χ^2 tests. The time-to-rescue medication will be summarized using Kaplan-Meier curves and compared between groups using stratified log-rank tests. Level of significance will be set at $\alpha=0.05$. JMP software and GraphPad will be used for the analyses and the graphs.

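### Time to rescue is compared by a stratified log-rank test with no stratum named, no commitment to use time-0 VAS and no effect size; a Cox model with continuous time-0 VAS is a cheap improvement

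*Combined protocol and SAP*

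**What the plan says.** Section 12.4 gives the whole method for this endpoint: "The time-to-rescue medication will be summarized using Kaplan-Meier curves and compared between groups using stratified log-rank tests". No section says what the strata are. Allocation is described without strata in Section 7 ("Eligible subjects will be randomized in a 1:1 ratio to one of the three study intervention arms") and in Section 10.1, so they cannot be inferred from the randomization. Section 12.3 names two baseline factors, for another purpose: "we will specifically assess for age and sex balance and perform sensitivity analyses, if indicated".

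On the link between pain and rescue, Section 11.1 says that "subjects will be instructed to request rescue medication when their pain becomes uncomfortable". The same sentence opens by noting that endurance of pain differs between patients, and the next encourages a wait of at least 60 minutes before rescue. Section 8.1 leaves rescue to the provider's discretion; Section 10.3 gives it at the patient's request.

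Pain at dosing is collected. Section 3.2 states: "Patients will report their pain level using a 100mm Visual Analogue Scale (VAS) at 0, 15min, 30min". Entry under Section 6.2 requires "Permanent tooth with moderate to severe odontogenic pain, i.e. ≥30 on a 100mm VAS", so baseline pain can lie anywhere from 30 to 100 mm.

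Section 10.3 offers the time-to-rescue analysis as the response to the effect of rescue analgesics on pain. Section 12.2 describes a pilot meant to find the effect size for a definitive trial: "We plan to enroll a convenience sample of N=22/group".

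**The concern.** Two things are missing from the rescue comparison.

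- **Baseline pain.** If patients ask for rescue when pain becomes uncomfortable, pain at dosing is a natural candidate to predict when they ask. It is on file as a number for every patient, yet the plan does not commit to using it. At 22 per arm, a chance difference in baseline pain feeds into the rescue curves, and predictable spread in rescue times is treated as noise.
- **An effect size.** A log-rank test returns a p-value. The pilot exists to inform the design of a later trial, for which a hazard ratio with its interval is the useful output. This holds whether or not baseline pain proves prognostic.

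The point concerns the choice of method for time to rescue. It does not touch the VAS models, and it does not claim that a stratified log-rank test is invalid.

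**Working it through.** **Plan's own figure.** There is none to reproduce. The 22 per group is declared a convenience sample, with no effect size, rescue rate, event count or power.

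**Inputs from the documents.** 22 per arm; alpha 0.05 (two-sided assumed); VAS at time 0, range 30 to 100 mm; rescue observed for 3 hours, taken as the censoring time.

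**Inputs assumed.** VAS mean 60 and SD 18 mm; placebo rescue by 3 h of 50, 70 or 80%; hazard ratio 0.4 for CBD against placebo; log hazard of rescue rising by b per SD of VAS, with b from 0 to 1.0 (hazard ratio per SD of exp(0.4) = 1.5, exp(0.7) = 2.0, exp(1.0) = 2.7).

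**Chance imbalance.** The difference between two arm means has standard deviation 18 × √(2/22) = 5.4 mm, or 0.30 SD. At b = 0.7 an imbalance of that size shifts the apparent hazard ratio by a factor of about exp(0.7 × 5.4/18) = exp(0.21) = 1.23. A difference above 0.5 SD between two given arms has probability 2 × [1 − Φ(0.5/0.3015)] = 2 × [1 − Φ(1.66)] = 9.7%; for at least one of the three pairs it is about 22% by simulation.

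**Power, 22 v 22, hazard ratio 0.4 (%).** The stratified column uses VAS split in two. The 70% rows have 3,000 runs, rescue possible from 0.5 h, and a Wald test for Cox. The 80% rows and the first 50% block have 5,000 runs and a score test. The last block has 2,000 runs and a Wald test.

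| Placebo rescue | VAS effect per SD | Unstratified log-rank | VAS-stratified log-rank | Cox, continuous VAS |
|---|---|---|---|---|
| 70%, Wald | b = 0 | 60 | 57 | 58 |
| | b = 0.4 | 58 | 60 | 60 |
| | b = 0.7 | 49 | 55 | 59 |
| | b = 1.0 | 40 | 49 | 58 |
| 80%, score | HR 1.0 | 68.4 | 66.3 | 67.9 |
| | HR 1.5 | 62.4 | 63.7 | 67.6 |
| | HR 2.0 | 54.4 | 61.1 | 69.1 |
| | HR 2.5 | 45.7 | 57.6 | 68.8 |
| 50%, score | HR 1.0 | 42.9 | 41.5 | 42.8 |
| | HR 1.5 | 42.3 | 42.7 | 44.4 |
| | HR 2.0 | 37.7 | 40.1 | 44.7 |
| | HR 2.5 | 33.7 | 38.5 | 44.1 |
| 50%, Wald | b = 0 | 43 | 42 | 39 |
| | b = 0.4 | 45 | 45 | 43 |
| | b = 0.7 | 42 | 43 | 43 |
| | b = 1.0 | 36 | 42 | 45 |

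Cox against the unstratified log-rank:

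- 70% rescue: −2, +2, +10 and +18 points as b rises.
- 80% rescue: −0.5, +5.2, +14.7 and +23.1 points.
- 50% rescue: +1 (Wald) to +7 (score) at a moderate link, +9 to +10 at a strong one.

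Cox against the VAS-stratified log-rank: about 0 to 9 points at 70% rescue, up to 11 at 80%, and from −3 to about +6 at 50%.

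**Departures from the model (70% rescue).** If 70% of would-be early requesters wait until 60 minutes, power at b = 0.7 was 52 / 57 / 57% in one set of runs and 52 / 55 / 60% in another; at b = 1.0 it was 43 / 53 / 56% and 42 / 50 / 55%. The gain over VAS stratification is then 0 to 5 points. If the drug effect starts only at 1.25 h, the three tests are level at 14 to 19%.

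**False-positive rate (5,000 runs).** Unadjusted 4.5 to 5.9%, VAS-stratified 4.7 to 6.0%, adjusted Cox 5.3 to 6.1%.

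**Context.** Schoenfeld events for 80% power at hazard ratio 0.5 are 4 × (1.96 + 0.84)² / (ln 0.5)² ≈ 66, in a two-arm comparison with 44 patients.

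**The case against.** **The plan may already use baseline pain.** A reader might infer from Section 12.4 that pain at dosing is ignored. The text does not support that: the test is stratified on something unnamed, and VAS could be it. A reader might equally infer that the strata are age and sex. Section 12.3 names those only for a balance check and possible sensitivity analyses. What stands is that the stratum is undefined and VAS is not specified.

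**Baseline VAS may predict rescue poorly.** It is tempting to call it a leading predictor. The documents give no association between VAS and rescue, and Section 11.1 stresses individual endurance and encourages a 60-minute wait. Provider discretion in Section 8.1 could weaken the link further. This objection stands: the link is plausible, its strength unknown.

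**The power gain is conditional.** This also stands. A flat statement that adjustment is more powerful goes beyond the evidence. With a weak link there is little or no gain; with a late-onset effect there is none. The largest gains come from data generated under the model being recommended.

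**Cox is partly a preference.** It estimates a hazard ratio conditional on baseline pain and assumes proportional hazards, which the encouraged wait may strain. That is a reason to keep the unadjusted test in view. It does not answer the absence of an effect size in a pilot that exists to estimate one.

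**Conclusion.** The point holds as a low-severity improvement. Section 12.4 leaves the stratum undefined, does not commit to time-0 VAS, and yields no effect size for time to rescue. The firm benefits are an estimate with its interval and protection against chance imbalance in baseline pain, where one standard deviation between two arms is about 5.4 mm if the VAS SD is 18 mm.

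The power benefit depends on assumptions outside the documents. Over an unstratified log-rank it runs from none with a weak link to about 20 points with a strong link and 70 to 80% placebo rescue. If VAS does not predict rescue, the loss was 2 to 4 points with a Wald test and about nil with a score test.

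Nothing here invalidates the plan. Time to rescue is not among the primary or secondary outcomes in Section 3, and the comparison is underpowered with or without adjustment.

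**What to change.** In Section 12.4:

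- Keep the Kaplan-Meier curves.
- Pre-specify a Cox model with arm and continuous time-0 VAS, reporting the hazard ratio and 95% CI for each CBD dose against placebo. Name the test (score or Wald) and say that proportional hazards will be examined.
- Report the unadjusted log-rank test alongside. If a stratified test is retained, name its strata.

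This costs a sentence or two and needs no new data. The price is the proportional-hazards assumption, a hazard ratio conditional on baseline pain, and about 2 to 4 points of power under a Wald test if VAS does not predict rescue.

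Sections 8.1 and 10.3 differ on whether provider or patient triggers rescue. They should be reconciled, because that defines the event being analysed.
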